7.0 DEMOGRAPHICS AND OTHER BASELINE CHARACTERISTICS

Demographic parameters (age; age group (<65 vs ≥ 65, race; ethnicity; sex), baseline characteristics (wearing contact lenses before seven days prior to the study) and other disease characteristics (Sjogren's syndrome) will be summarized descriptively by treatment group and overall for the ITT populations. Continuous variables will be summarized by number of patients and mean, SD, Q1/Q3, median, minimum, and maximum values. Categorical variables will be summarized by number and percentage of patients. A subject listing of demographics and baseline characteristics will be provided.

Medical and surgical histories will be coded using the *Medical Dictionary for Regulatory Activities*, version 20.1 or newer. The number and percentage of patients with Ocular and Non-Ocular medical and surgical histories at baseline in each system organ class and preferred term will be summarized by treatment group for the Safety Population, separately. A subject listing for Surgical and Medical Histories will be provided.

Prior medication is defined as any medication taken before the date of the first dose of study treatment. *Concomitant medication* is defined as any medication taken on or after the date of the first dose of study treatment.

Both prior and concomitant medications will be coded using The Anatomical-Therapeutic-Chemical classification text from World Health Organization (WHO) Drug Dictionary. The use of prior and concomitant medications will be summarized by the number and percentage of patients in each treatment group for the Safety Population. If a patient took a specific medication multiple times or took multiple medications within a specific therapeutic class, that patient would be counted only once for the coded drug name or therapeutic class. Formulations (including salts, esters, etc) containing the same active ingredient will be pooled under the coded drug name of the base compound. Medications containing multiple active ingredients of different coded drug names will be reviewed during the study and may be pooled under a single coded drug name for analyses. A subject listing for prior and concomitant medications will be provided.

The Anatomical-Therapeutic-Chemical classification text from World Health Organization (WHO) Drug Dictionary, MAR17 or newer, will be used to classify prior and concomitant medications by therapeutic class and drug name.

A listing of randomized data will be presented. A listing of the significant protocol deviations reported will be provided. A significant deviation includes the deviation coded as 'Inclusion/Exclusion and Randomization' and 'Improper Protocol Procedures at Site (missed, repeated, not per protocol)'.

8.0 EXTENT OF EXPOSURE AND TREATMENT COMPLIANCE

8.1 EXTENT OF EXPOSURE

Exposure to the study treatment for the Safety Population during the study period will be summarized for [treatment duration, calculated as the number of days from the date of the first application dose of study treatment to the date of the last application of study treatment, inclusive. Descriptive statistics will be presented by treatment group and overall.

8.2 MEASUREMENT OF TREATMENT COMPLIANCE

A subject listing will be prepared that provides the treatment assignment for all randomized or treated subjects. The study completion status and the reason selected for subjects that did not complete the study as planned is displayed in the discontinuation listing.

9.0 **EFFECTIVENESS ANALYSES**

9.1 **PRIMARY EFFECTIVENESS PARAMETER(S)**

This study does not include any effectiveness measures since it is an exploratory pilot study.

9.2 **SECONDARY EFFECTIVENESS PARAMETER(S)**

Not applicable.

[REDACTED]

[Redacted text block]

[REDACTED]

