2.0 STUDY OBJECTIVES

The primary objective of this study is to compare the safety and efficacy of TrueTear (intranasal tear neurostimulation) to standardized moist heat compress (Thermalon Dry Eye Compress) for the treatment of Meibomian Gland Disease (MGD).

[figure not shown]

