3.0 CLINICAL HYPOTHESES

[figure not shown]
Thirty days of TrueTear application provides efficacious treatment of MGD compared to moist heat compress control as measured by signs and/or symptoms of MGD.

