8.2 Masking

Because the two devices are dissimilar and administered in very different ways, it will not be possible to mask the participant or the Investigator to the intervention assignment. As a means of minimizing bias where feasible, de-identified videos from the Tearscope assessment (lipid layer thickness) will be graded using the Guillon scale in a masked fashion.

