3.0 INTRODUCTION

This statistical analysis plan (SAP) provides a more technical and detailed elaboration of the statistical analyses of the effectiveness and safety data as outlined and/or specified in the final [protocol](#) of Study 1919-610-019 (version dated June 1, 2017). Specifications of tables, figures, and data listings are contained in a separate document.

[figure not shown]
Study 1919-610-019 is a prospective, open-label, randomized, parallel two-arm study conducted at up to two sites in patients at least 22 years of age who have a Standard Patient Evaluation for Dryness (SPEED) [REDACTED]. In at least one eye, the participants need to meet all of the objective measure in the same eye:

[figure not shown]
- A basal Schirmer test of \geq [REDACTED]
[REDACTED]
- [REDACTED]
- Tear film breakup time (TBUT) [REDACTED]
[REDACTED]

The length of this study will be approximately 44 days. Signed informed consent from the patient will be obtained before any study-related procedures are begun. At the Screening Visit, patients who provide written informed consent will be assigned a screening number. At the day of randomization (Day 0), patients meeting the entry criteria will be randomized (1:1 ratio) to either the TrueTear or moist heat compress control treatment groups. Following the initial application of treatment in clinic at Day 0, participants will apply the randomized treatment for approximately 30 days.

Effectiveness and safety assessments will be conducted at the clinic at Screening, Baseline, Day 7, Day 14 and Day 30.

The schedule of evaluations for Study 1919-610-019 is presented in [Table 3–1](#).

4.0 **OBJECTIVES**

The primary objective of this study is to compare the safety and effectiveness of TrueTear (intranasal tear neurostimulator) to standardized moist heat compress (Thermalon Dry Eye Compress) for the treatment of Meibomian Gland Disease (MGD).

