5.3 DATA COLLECTED BUT NOT ANALYZED

The following variables collected on the CRF but not addressed in the analysis will be listed in the subject data listing without statistical summary or hypothesis testing: dates that informed consent was signed, dates of informed consent version, reason for unscheduled visits; medical status update, and required examination forms.

6.0 **PATIENT DISPOSITION**

The frequency (count and percent) of patients randomized, treated, completed study and prematurely discontinued during the study period will be presented for each treatment group and overall. The number of patients screened will be summarized overall only.

The frequency of patients who complete the study period and of patients who prematurely discontinue during the same period will be presented on the ITT Population. The reasons for premature discontinuation from the study period as recorded on the termination pages of the case report forms will be summarized (number and percentage) by treatment group for the ITT Population. All patients who prematurely discontinue during the study period will be listed by discontinuation reason for the ITT Population.

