10.0 SAFETY ANALYSES

The safety analysis will be performed using the Safety Population. The safety parameters will include adverse events (AEs) and other safety measurements defined in the protocol including corrected distance visual acuity or slip lamp biomicroscopy findings. For each safety parameter, the last nonmissing safety assessment before the first dose of study treatment will be used as the baseline for all analyses. Continuous variables will be summarized by number of patients and mean, SD, median, minimum, and maximum values. Categorical variables will be summarized by number and percentage of patients.

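### Does SAP 9.1 leave the trial without effectiveness measures, against its own primary objective?

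*SAP*

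**What the plan says.** SAP 9.1, headed as the section on primary effectiveness parameters, consists of one sentence: "This study does not include any effectiveness measures since it is an exploratory pilot study". SAP 9.2, on secondary parameters, is marked not applicable. A redacted block follows before section 10.

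Elsewhere the documents treat effectiveness as something that is measured and compared:

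- SAP 4.0: "The primary objective of this study is to compare the safety and effectiveness of TrueTear", with the moist heat compress as comparator.
- SAP 3.0: "Effectiveness and safety assessments will be conducted at the clinic at Screening, Baseline, Day 7, Day 14 and Day 30".
- Protocol 2.0: "The primary objective of this study is to compare the safety and efficacy of TrueTear", against the same comparator.
- Protocol 3.0: "Thirty days of TrueTear application provides efficacious treatment of MGD compared to moist heat compress control", judged on signs and/or symptoms.
- Protocol 8.2: "de-identified videos from the Tearscope assessment (lipid layer thickness) will be graded using the Guillon scale in a masked fashion".
- Protocol 11.2 sets a null hypothesis of no difference between the devices on the exploratory measures. The synopsis gives two-sided testing at 0.05 as the general rule.

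Protocol 11.1 and SAP 12.0 say that this is a proof-of-concept study whose size was not formally calculated. SAP 15.0 records no changes from the protocol's analyses.

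**The concern.** The same SAP states a comparative effectiveness objective and then denies that the study measures effectiveness. On a literal reading, the lipid layer grading and the tear film breakup time described in protocol 15.2.3 have no home in the readable SAP. Section 9.1 denies such measures. Section 10.0 ("The safety parameters will include adverse events (AEs) and other safety measurements defined in the protocol") does not name them. Section 5.3, which covers variables "collected on the CRF but not addressed in the analysis will be listed in the subject data listing without statistical summary or hypothesis testing", does not name them either.

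What seemed to be at stake was the study report. SAP 4.0 and protocol 2.0 and 3.0 state the objective or hypothesis without an exploratory qualifier in their readable text, and no readable section names one measure that decides whether the objective is met. A report could then present a single nominal p<0.05 as meeting the primary objective, in a trial where neither participants nor the Investigator are masked.

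**Working it through.** The question is one of consistency between texts, so the main check compares them.

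**1. Is there a literal conflict?** Yes. SAP 3.0 and 4.0 and protocol 2.0, 3.0 and 11.2 all presuppose effectiveness measures, and SAP 9.1 says there are none. This holds whatever the redacted block contains.

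**2. What does the sentence mean where it stands?** Its heading concerns primary parameters, the next heading concerns secondary ones, and redacted text follows within section 9. The reason it gives, that the study is an exploratory pilot, explains why no primary parameter is chosen. It does not explain why nothing would be measured. The reading that fits the heading, the reason given and protocol 11.2 is that no primary or secondary parameter is designated and that the measures are exploratory.

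**3. Do the measures lack a home?** The readable text does not show that. The redacted block lies where exploratory parameters would be expected. Section 5.3 names specific items that are listed without analysis: consent dates, consent version dates, reasons for unscheduled visits, the medical status update and the required examination forms. Lipid layer grade and breakup time are not among them, which suggests that they are analysed somewhere. Breakup time is readable only as an eligibility criterion and a procedure, so calling it an effectiveness outcome is itself an inference.

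**4. What would rewording change?** If the redacted block specifies exploratory measures, their analysis is already fixed and the rewording alters nothing. If it does not, the rewording still adds no analysis. Any gap would then be a different point, which cannot be judged on redacted text.

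**5. Size.** The plan's only figures are about 70 enrolled and about 60 completing, with 1:1 allocation. No effect size, SD, power or dropout rate is given, so no calculation can be reproduced. The two counts imply attrition of 1 − 60/70 = 14.3%.

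For context, take a continuous measure with one value per participant, a common SD and no covariate adjustment. The 95% confidence interval half-width in SD units is t(0.975, n1+n2−2) × √(1/n1 + 1/n2):

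| Completers per arm | Calculation | Half-width |
|---|---|---|
| 30 and 30 | 2.0017 × √(2/30) | 0.517 SD |
| 25 and 35 | 2.0017 × √(1/25 + 1/35) | 0.524 SD |
| 35 and 35 | 1.9955 × √(2/35) | 0.477 SD |

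A result exactly at p = 0.05 with 30 per arm would be an observed difference of 0.517 SD, with an interval from 0 to 2 × 0.517 = 1.03 SD. By the normal approximation, the difference detectable with 80% power is (1.960 + 0.842) × √(2/30) = 0.72 SD.

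These figures describe a small proof-of-concept trial. They are the same before and after any rewording of 9.1.

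**The case for a change.** The best case for a change is that the sentence is false as written and that no redacted text can make it true. If the hidden block defines exploratory measures, 9.1 is wrong. If it does not, 9.1 conflicts with 3.0 and 4.0. An exploratory aim explains the absence of a primary parameter but does not make the measures disappear. Section 9.1 is also where a reader would look for the measure that decides the objective, and correcting it would cost a few sentences.

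The point about wording stands: the sentence should have been confined to primary parameters. The consequences drawn from it do not stand.

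- **Misreporting.** The predicted claim is conjecture. The proof-of-concept or exploratory status is in the title, protocol 11.1 and 11.2, and SAP 9.1 and 12.0. Protocol 8.2 openly states the lack of masking, which is a separate matter.
- **Missing qualifier.** That protocol 2.0 and 3.0 lack an exploratory qualifier cannot be fully confirmed, because figures are missing from both sections in the text supplied.
- **Recasting the objective as estimation.** This is a preference about framing and fits poorly with protocol 11.2, which states a hypothesis test. Dropping the test would be a departure to record in SAP 15.0.
- **Confidence intervals.** A request for them depends on text that cannot be seen. The half-widths above may also not suit the one clearly visible masked outcome, which is graded on a scale.

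**Conclusion.** No change to the plan is needed. SAP 9.1 contains a clerical overstatement, and its heading, the entry that follows it and protocol 11.2 let an analyst read it correctly as designating no primary effectiveness parameter. Its effect on planned analyses, error rates and results is nil. The interval half-widths of about 0.48 to 0.52 SD follow from the planned size, not from the sentence.

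The conclusion rests on reading 9.1 in the light of its heading, and on not treating redacted text as absent from the plan. Confidence is high that the wording is loose and that correcting it would change no analysis. What the redacted block contains remains unknown.

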10.0 SAFETY ANALYSES

The safety analysis will be performed using the Safety Population. The safety parameters will include adverse events (AEs) and other safety measurements defined in the protocol including corrected distance visual acuity or slip lamp biomicroscopy findings. For each safety parameter, the last nonmissing safety assessment before the first dose of study treatment will be used as the baseline for all analyses. Continuous variables will be summarized by number of patients and mean, SD, median, minimum, and maximum values. Categorical variables will be summarized by number and percentage of patients.

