10.1 ADVERSE EVENTS

Adverse events will be coded by system organ class and preferred term using the *Medical Dictionary for Regulatory Activities*, version 20.1 or newer.

An AE will be considered a treatment-emergent adverse event (TEAE) if it was present one or after the first application of study treatment or was present before the date of the first application of study treatment and increased in severity or became serious on or after the first application of study treatment.

An AE will be considered a treatment-emergent serious AEs (TESAE) if it is a TEAE that additionally meets any SAE criteria.

The number and percentage of patients reporting TEAEs and treatment-related TEAEs in each treatment group will be tabulated by system organ class and preferred term, separately. If more than 1 AE is coded to the same preferred term for the same patient, the patient will be counted only once for that preferred term using the greatest severity.

A summary table will be provided for subjects with TEAE, TESAE, death and subjects with TEAEs leading to discontinuation if 5 or more participants reported such events. A subject listing of all AEs will be presented.

11.0 **INTERIM ANALYSIS**

No interim analysis is planned for this study.

12.0 **DETERMINATION OF SAMPLE SIZE**

As this is a proof of concept study, no formal calculation of sample size was conducted. Approximately 70 participants will be enrolled to achieve approximately 60 completed.

13.0 **STATISTICAL SOFTWARE**

Statistical analyses will be performed using version [REDACTED]
[REDACTED]

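### The primary objective is to compare safety, but SAP section 10 specifies only descriptive summaries and no between-group difference with a confidence interval

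*SAP*

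**What the plan says.** Both documents set a comparative objective. Protocol 2.0: "The primary objective of this study is to compare the safety and efficacy of TrueTear (intranasal tear neurostimulation) to standardized moist heat compress". SAP 4.0: "The primary objective of this study is to compare the safety and effectiveness of TrueTear (intranasal tear neurostimulator) to standardized moist heat compress".

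The analysis of safety is in SAP 10.0 and 10.1, on the Safety Population. For continuous measures, SAP 10.0 says: "Continuous variables will be summarized by number of patients and mean, SD, median, minimum, and maximum values". For categorical measures: "Categorical variables will be summarized by number and percentage of patients". For adverse events, SAP 10.1 says: "The number and percentage of patients reporting TEAEs and treatment-related TEAEs in each treatment group will be tabulated by system organ class and preferred term". It adds a subject listing and an overall summary table, at least part of which depends on 5 or more participants reporting the events concerned.

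The hypotheses in Protocol 11.2 are worded for the exploratory measures and do not name safety. SAP 15.0 records no changes from the analyses in the protocol. SAP 3.0 places the specifications of tables, figures and listings in a separate document, which is not among those available.

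**The concern.** A primary objective that says compare calls for a stated contrast. SAP section 10 states none: no risk difference, no difference in means, no interval. The safety part of the primary objective would then be judged by looking at two columns of percentages.

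With about 35 participants per arm, that judgement is fragile. Equal or near-equal percentages look reassuring, yet remain compatible with a sizeable excess in either arm. The same holds for rows with no events. An interval beside each contrast shows the reader how much excess the data leave open.

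**Working it through.** **Is there a figure in the plan to reproduce?** No. Protocol 11.1 and SAP 12.0 state that no formal sample size calculation was done, and neither gives an adverse event rate, a safety margin or a precision target. The only figures are about 70 enrolled, about 60 completing, and 1:1 allocation.

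**Inputs**
- n = 35 per arm, from 70/2. The Safety Population needs only one device application, so this is close to its expected size.
- n = 30 per arm, from 60/2, as a lower case.
- Event counts: assumptions for illustration, because the documents give none.

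**Formulas.** For x events in n, with p = x/n and z = 1.96, the Wilson limits l and u are [p + z²/(2n) ± z√(p(1−p)/n + z²/(4n²))] / (1 + z²/n). The Newcombe interval for d = p1 − p2 runs from d − √((p1−l1)² + (u2−p2)²) to d + √((u1−p1)² + (p2−l2)²).

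**Wilson limits, n = 35**
- 0/35: 0 to 0.0989
- 3/35 = 0.0857: 0.0296 to 0.2238
- 4/35 = 0.1143: 0.0454 to 0.2595
- 7/35 = 0.2000: 0.1004 to 0.3589

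**Risk differences, n = 35**
- 7 v 7: 0 ± √(0.0996² + 0.1589²) = ±0.188
- 3 v 3: 0 ± √(0.0561² + 0.1381²) = ±0.149
- 0 v 0: 0 ± 0.0989 = ±0.099
- 7 v 3: 0.114; lower 0.1143 − √(0.0996² + 0.1381²) = −0.056; upper 0.1143 + √(0.1589² + 0.0561²) = 0.283

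In percentage points:

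| Assumed events, TrueTear v compress | Difference | 95% CI, 35 per arm |
|---|---|---|
| 7 v 7 | 0 | −19 to +19 |
| 3 v 3 | 0 | −15 to +15 |
| 0 v 0 | 0 | −10 to +10 |
| 7 v 3 | +11 | −6 to +28 |

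**Sensitivity to n.** At 30 per arm, 7 v 7 gives ±21 points, 3 v 3 gives ±17 and 0 v 0 gives ±11.

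**Zero events in one arm.** The exact two-sided 95% upper limit is 1 − 0.025^(1/35) = 0.100, or 10.0%. At 30 it is 1 − 0.025^(1/30) = 0.116, or 11.6%.

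**The 5-participant condition.** The scope of this condition in SAP 10.1 is unclear. If it governs the discontinuation row and counts both arms together, 4 v 0 would fall below it. That split is a difference of +11 points, with a 95% CI from 0.1143 − √(0.0689² + 0.0989²) = −0.006 to 0.2595, that is −1 to +26 points.

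**The case against.** **This is convention for a small study.** The trial is a proof of concept without a formal sample size, SAP 9.1 calls it an exploratory pilot, and no safety hypothesis or margin is stated. Tabulating adverse events by arm is normal in that setting. This stands as an argument against p-values and against treating the omission as a serious flaw. It does not reconcile a comparative objective with a purely descriptive plan. Rewording the safety objective as descriptive would also remove the mismatch, but would tell the reader less.

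**A reader might infer that the trial yields no estimate of the safety difference.** The documents do not support that. SAP 10.1 gives numbers and percentages per arm, from which anyone can compute a crude difference and an interval, as done above. What is missing is a pre-specified, displayed contrast.

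**A reader might infer that only counts and percentages are planned.** That is also too strong, since SAP 10.0 includes mean, SD, median and range for continuous measures.

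**The complete method may not be visible.** The table specifications are in a document that was not available, and blacked-out text follows the general statistical methods in the protocol synopsis. A difference with an interval could appear there. SAP 10.0 and 10.1 themselves show no redaction, so the point is limited to what those sections specify.

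**No passage plans to conclude that safety is similar.** Correct. The risk lies in how bare percentages may be read, not in a stated intention.

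**Intervals add no data, and the event counts above are invented.** Both are true. The intervals show the imprecision that bare percentages leave out, and the counts only indicate its order of size.

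**Conclusion.** The point holds as a mismatch: the primary objective asks for a comparison of safety, and SAP 10.0 and 10.1 specify descriptive summaries without a between-group difference and confidence interval. It is a cheap improvement rather than an error in a number.

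The uncertainty left undisplayed is large. With 35 per arm, equal observed rates leave differences of about 10 to 19 points in either direction compatible with the data across the counts tried, and somewhat more with 30 per arm. This rests on 1:1 allocation of about 70 participants, nearly all of them in the Safety Population, and on assumed event counts. Whether the separate table specifications already include such a contrast is unknown.

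**What to change.** Add one paragraph to SAP 10.1. For each row below, report the TrueTear minus compress risk difference with a Newcombe 95% confidence interval and no p-value:

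1. participants with any TEAE;
2. participants with any ocular TEAE;
3. participants with any treatment-related TEAE;
4. participants with any TEAE leading to discontinuation.

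Four details need to go with it.
- Define ocular TEAE by MedDRA system organ class. SAP 10.1 has no ocular category; the ocular and non-ocular split appears only for medical and surgical history in SAP 7.0. This row is the closest to like for like, because the anticipated events in Protocol 9.6 are largely nasal or facial for TrueTear and only blurry vision for the compress.
- Show all four rows whether or not 5 or more participants report such events.
- Note beside the treatment-related row that the investigator judging relatedness is unmasked (Protocol 8.2), so the interval covers sampling error only.
- State that any comparative safety statement in the report will rest on these intervals. Align the table specifications with the SAP.

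The cost is one paragraph, one derivation rule and four table rows, from adverse event data already planned for collection. The downside is that the intervals will be wide and will limit any claim of similar safety.
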